Patients with previous diagnosis of histoplasmosis will not be considered for this study. We will also exclude pregnant or lactating woman, patients with renal failure (serum creatinine and urea >1.5 times the upper limit of normality), abnormal aminotransferases (up to >3 times the upper limit of normality), and patients with a previous serious reaction to a polyene antifungal drug. Patients who received more than one dose of a polyene antifungal drug in the last 48 hours will be excluded, as well as patients who refuse content to participate in the study. Patients diagnosed with histoplasmosis affecting the central nervous system will not be allowed to participate in the study. In addition, patients who are expected to die within 48 hours of enrolment will also be excluded, based on the judgment made by the attending physician. Patients diagnosed with tuberculosis will be excluded; as well those receiving drugs that cause significant drug-drug interaction (relative or absolute) with itraconazole.

Study settings

Six medical centers in Brazil, will recruit patients for this study: Santa Casa de Misericórdia de Porto Alegre, Hospital de Clínicas de Porto Alegre, Hospital Nossa Senhora da Conceição, Hospital de Doenças Tropicais, Hospital São Jose de Doenças Infecciosas, and Hospital Giselda Trigueiro.

Intervention

AIDS patients with DH will be randomized to one of three study arms: (i) single IV dose of L-AmB at 10 mg/kg; (ii) single IV dose of 10 mg/kg of L-AmB on day 1, followed by 5 mg/kg of L-AmB on day 3; and (iii) L-AmB at 3 mg/kg IV for 2 weeks. Induction therapy will be followed in all patients by oral therapy with itraconazole capsules at 400 mg/daily for a year.

Drug reconstitution and administration

L-AmB (AmBisome; Gilead Sciences, San Dimas, California, USA), a lyophilized liposomal preparation of amphotericin B, will be reconstituted according to the manufacturer's instruction and given intravenously at fixed doses, according to the randomization arm. L-AmB concentration should be of 0.2 mg/ml in 5% dextrose, and the drug should be infused over 2 hours, preferably in a central line. Patients will be monitored for the occurrence of infusion-related toxicity during and after drug infusion.

Primary endpoint

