Clinical and mycological successes will be the primary outcomes for this study. A successful clinical response to induction therapy will be defined according to, as a maximum daily temperature $<37.8^{\circ}\text{C}$ for 72 hours; no increase in severity of clinical signs, symptoms, or laboratory abnormalities attributable to histoplasmosis; and the resolution of at least one of the signs or symptoms of histoplasmosis that qualified the patient for study enrollment [7].

Primary study outcome will be determined at day 14 of the study.

Secondary endpoints

Overall mortality and investigator-attributable mortality due to histoplasmosis will be determined at day 14 of study. Overall Survival (OS) will also be determined at 12, 24, and 48 weeks of study. OS will be considered as the time from randomization until death from any cause.

Secondary endpoint will also include need for an additional antifungal course with L-AmB, during 24 weeks of follow up.

Median percentage of change in renal and hepatic function at 14 days will be compared with baseline values.

Frequency of infusion-related toxicity with L-AmB will be recorded.

Clearance of blood cultures will not be used as a criterion for mycological response in this study, due to the limited sensitivity of blood culture in histoplasmosis [19]. Fungal clearance will also not be used as a criterion for mycological response. Differently from cryptococcosis, in which fungal burden is easily obtained and quantified in cerebrospinal fluid samples,

in histoplasmosis commonly a single positive sample is obtained along patient investigation (e.g., microscopy, culture, and/or histopathology).

Non-culture laboratory markers have proved to be useful adjuncts in monitoring the response to systemic histoplasmosis [20, 21]. In this study, we will evaluate the effect of a decrease of at least 50% in *Histoplasma* urinary antigen concentrations [19] along the first 2 weeks of therapy as a secondary endpoint, and the association of such reductions with clinical response to antifungal therapy.

Rescue therapy

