The study protocol will allow patients to receive additional courses of L-AmB (at 3 mg/kg daily) in case the attendant physician suspect of absence of response with the induction regimen. This will apply for failing patients receiving a single 10 mg/kg of L-AmB; or 10 mg/kg on day 1, followed by 5 mg/kg on day 3. In these cases, L-AmB should be given up to a maximum period of 2 weeks. The estimated frequency of L-AmB as rescue therapy will be based on the frequency of failure with L-AmB at 3 mg/kg in patients with DH and AIDS (i.e., 12%) [7]. Considering that 66 patients will be evaluated in arms (i) and (ii) of the study (high-doses of L-AmB), in a pessimistic scenario we aim to provide 8 additional treatments with L-AmB.

Time for initiating ART

Physicians will be instructed to initiate ART as soon as possible in AIDS patients with DH, since immune reconstitution syndrome is uncommon in patients with DH [22]. In Brazil, initial ART consists of dolutegravir, lamivudine, and tenofovir. History of previous antifungal use and known resistance patterns will also be considered in the decisions about ART.

Statistical analyses

Descriptive statistics will be used to summarize the data. Mean, standard deviation, median, interquartile range and minimum and maximum will be described for continuous variables. Categorical variables will be summarized by absolute and relative frequencies. Kaplan-Meier method will be used in order to describe OS. Despite the non-comparative status of the

trial, exploratory comparisons will be performed across subgroups. Continuous variables will be compared using two sample t-test, paired sample t-test, Mann-Whitney test, Wilcoxon signed-rank test, one-way ANOVA or Kruskal-Wallis test, as appropriate and necessary. Categorical variables will be compared with Fisher exact test or chi-square test, as appropriate. All p-values will be two-sided.

We expect that the three arms will have the same clinical response. For each arm, when the sample size is 29, a two-sided 90% confidence interval will extend 10% from the observed proportion for an expected proportion of response equal to 88% [as extracted from the Johnson trial]. Considering a dropout of 10%, the sample size per arm will be 33. The total sample size for the study will be 99 patients. Data analysis will be performed using SPSS software.

Ethical aspects

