Conduction of this study is conditioned to ethical approval by local IRBs. Since this trial will not aim to modify any regulatory aspect related to L-AmB in Brazil, ANVISA (Brazilian Health Regulatory Agency) will not be consulted. The study will also be registered at clinicaltrials.gov.

Study activities

Clinical evaluations will take place at baseline, day 3, day 7, and day 14 (End of Study Visit). End of follow up will occur at week 48, and mortality will be determined at weeks 12, 24, and 48.

The study will recommend careful attention to hydration status, and close monitoring of renal function, hepatic function, and electrolytes. Unless clinically advisable, physicians are requested to give one liter of saline 0.9% solution intravenously before L-AmB infusion. Patients should also be on prophylaxis with daily trimethoprim-sulfamethoxazole.

Table 1 shows the procedures predicted for this study. Clinical and laboratory adverse events will be graded using the NIH DAIDS Toxicity Table [23]. Itraconazole therapeutic drug monitoring will be offered to sites at day 7 and day 14 of study. The attending physicians will use this information according to their personal judgment.

Table 1. Study activities.

	Baseline	Day 3	Day 7	Day 14	Week 12	Week 24	Week 48
Informed Consent	X						
History	X						
Physical Exam	X		X	X			
Maximum Temp	X	X	X	X			
Glasgow coma scale	X		X	X			
Chemistry (including magnesium) and blood counts	X		X	X			
HIV documentation	X						
CD4 count determination							
Pregnancy Test	X						
Chest X-ray	X			X			
Study Drug accountability	X						
Concomitant medications	X	X	X	X			
Adverse Events		X	X	X			
Survival determination				X	X	X	X
Molecular test for TB	X						
Urine for Histo antigen test	X		X	X			
Histoplasma PCR (as needed)	X						
Fungal culture (as needed)	X						
Microscopy (as needed)	X						
Histopathology (as needed)	X						
Itraconazole TDM			X	X			
Lysis centrifugation (if available)	X						
Study responde determination				X			
Need for additioal course of L-AmB				X	X		

Study Plan Schedule Strategy

Table 2 shows the predicted timeline for this study.

Table 2. Study plan.

References

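### The 24-week endpoint on additional L-AmB courses has no scheduled recording point after week 12

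*Combined protocol and SAP*

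**What the plan says.** The Secondary endpoints section sets the window without restricting it to any arm: "Secondary endpoint will also include need for an additional antifungal course with L-AmB, during 24 weeks of follow up".

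The Study activities section places the clinical visits early: "Clinical evaluations will take place at baseline, day 3, day 7, and day 14 (End of Study Visit"). For later follow-up it says that "mortality will be determined at weeks 12, 24, and 48".

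Table 1 has columns for baseline, days 3, 7 and 14, and weeks 12, 24 and 48. The relevant rows are:

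- "Need for additioal course of L-AmB": marked at day 14 and week 12 only.
- "Concomitant medications": last marked at day 14. The adverse events row also ends there.
- "Survival determination": marked at day 14 and weeks 12, 24 and 48.

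The Rescue therapy section allows further L-AmB at 3 mg/kg daily, for at most 2 weeks, when the physician suspects non-response. It limits this to the two high-dose arms: "This will apply for failing patients receiving a single 10 mg/kg of L-AmB", or the two-dose regimen. The third arm is described under Intervention as "iii) L-AmB at 3 mg/kg IV for 2 weeks".

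**The concern.** The endpoint asks about 24 weeks, but the schedule asks the question for the last time at week 12. Survival can be established at week 24 without asking about treatment. A patient re-treated at week 16 and alive at week 24 would satisfy every scheduled item and leave no record of the course. With six centres, an item that nobody is assigned to collect may be asked at some sites and not at others.

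What is at stake is the meaning of one secondary result. The trial asks whether one or two large doses can replace two weeks of induction, and late re-treatment is relevant to that. Under-recording would make re-treatment look rarer than it was over the stated period. Start dates and reasons may also be hard to recover once follow-up has closed.

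A smaller matter is wording. The plan does not say what counts as an additional course in the two-week arm, where 3 mg/kg is already the assigned treatment.

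**Working it through.** **1. The plan's own figure for additional courses.** The Rescue therapy section uses a 12% failure frequency and 66 patients in arms (i) and (ii): 66 × 0.12 = 7.92, which rounds to the stated 8. The figure reproduces. It is a drug-supply estimate for non-response to induction in two arms. It is not a 24-week re-treatment rate for 99 patients, so it is not used below.

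**2. Endpoint window against schedule.**

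- Window (Secondary endpoints): 24 × 7 = 168 days.
- Last mark for the item (Table 1): week 12, or 12 × 7 = 84 days.
- Time after the last mark: 168 − 84 = 84 days, and 84/168 = 50%.

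This is a share of calendar time, not of events.

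**3. Could another row capture a later course?** The only rows of Table 1 marked after day 14 are survival (weeks 12, 24 and 48) and the item itself (week 12). Concomitant medications and adverse events stop at day 14, and drug accountability is marked at baseline only. At week 24 survival is therefore the only scheduled item. The text agrees: visits run to day 14, and mortality is the only later assessment it names.

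**4. Could a mark have been lost when the table was read?** The CD4 row has no marks at all, so a loss, or a drafting slip, is possible somewhere in the table. Against that, the survival row is marked at exactly the weeks the text gives. The columns are therefore aligned, and the week-24 column exists and is in use.

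**5. Size.** The documents give no rate of courses starting in weeks 12 to 24. Let r be the assumed proportion of patients whose first additional course starts in that period. If none of these is recorded, the expected number missed is 33r per arm and 99r overall:

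- r = 0%: 0 per arm, 0 overall.
- r = 2%: 33 × 0.02 = 0.7 per arm; 99 × 0.02 = 2.0 overall.
- r = 5%: 33 × 0.05 = 1.7 per arm; 99 × 0.05 = 5.0 overall.
- r = 10%: 33 × 0.10 = 3.3 per arm; 99 × 0.10 = 9.9 overall.

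These values of r are assumptions to show scale. Nothing in the documents favours one of them.

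**The case against.** The best reply is that the window is stated plainly, a week-24 contact already exists in every arm, and sites would naturally ask. On this view one mark is missing, possibly only from the copy that was read. The silence of the Study activities text also proves little, because it likewise omits the week-12 check that Table 1 does schedule. Non-response to at most two weeks of induction should mostly show itself early, so few courses may start after week 12. If the study supplies rescue drug, supply records might give a second trace, although the protocol does not describe this.

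Much of that stands. It limits the likely size of the problem and makes the remedy small. It does not remove the conflict: the existing contact makes collection possible, but nothing requires it.

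Two stronger readings are tempting, and the documents support neither.

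- A reader might infer that the two-week arm is fixed at zero events, so that any comparison is biased against the short regimens by a calculable amount. The endpoint has no arm restriction. In ordinary use an additional course is L-AmB beyond the assigned regimen, in any arm. The rescue text governs who is offered rescue, not what is counted, and nothing prohibits extending or restarting L-AmB in arm (iii). The trial is called non-comparative, the Statistical analyses section names no test of this endpoint, and arm (iii)'s rate is not given. A false-positive probability would therefore rest on invented inputs. More L-AmB after a one-dose strategy is also partly a real outcome of that strategy.
- A reader might apply the 12% to all 99 patients and assume that a large share of courses start late. That figure is a failure rate used to budget rescue in two arms, and the documents give no late share.

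**Conclusion.** The point holds as a conflict between an endpoint and its schedule. Half of the 24-week window (84 of 168 days) lies after the last scheduled recording of additional L-AmB, and no other scheduled item records treatment in that half. If sites follow Table 1 exactly, the reported 24-week figure is in effect a 12-week figure in all three arms.

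This rests on Table 1 as read, and the agreement of the survival row with the text makes a lost week-24 mark unlikely. The number of missed courses cannot be derived and could be small or nil.

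The counting question in arm (iii) is only a wording gap. It does not establish a biased comparison, and it gives no reason to rule out a between-arm test.

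The impact is limited to one secondary endpoint. The day-14 primary outcome and the sample size are unaffected. The change is still worth making because it costs so little.

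**What to change.** Add a week-24 mark in Table 1 for additional L-AmB, at the survival contact already planned. Ask whether any L-AmB was given since week 12, with start date and reason. If the sponsor's own copy of the table already carries this mark, only the question wording needs checking.

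As a minor clarification, add one sentence to Secondary endpoints: L-AmB beyond the assigned regimen counts in every arm, including extension past 2 weeks or restart in arm (iii). When reporting by arm, note that the protocol offers rescue only in arms (i) and (ii). Rescue eligibility need not change.

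The cost is one question at an existing contact, one sentence of definition and one reporting note. No extra visits, patients or drug are needed.

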these encouraging data, the strategy of using single high dose of L-AmB has never been tried in histoplasmosis.

Research Justification

DH is an endemic disease that frequently occurs in institutions with no access to modern diagnostic tests and that have limited availability of L-AmB. If a strategy of less frequent, high doses of L-AmB shows activity in DH, this will allow for reducing the cost of treatment in developing countries, in addition to improving safety and tolerability. Based on what has been published so far, safety does not seem to be a concern with high single doses of L-AmB. Results of this study may serve as a basis for a future phase III randomized comparative trial.

Objectives

To determine and compare the activity and safety of three regimens of L-AmB, as induction therapy of DH in AIDS patients, as well as to determine the safety of the three regimens.

Methods

Trial design

This will be a prospective randomized non-comparative multicenter open label trial of induction therapy for DH in AIDS, followed by oral therapy with itraconazole.

The total sample size planned is 99 patients (33 patients per study arm). This sample size considers 10% of dropout.

The study will be conducted in compliance with the declaration of Helsinki, as well as ICH GCP guidelines. Participation in the study will require written consent. The study will be registered at www.clinicaltrials.gov, before trial initiation and patient recruitment.

Participants

We will include adult (≥ 18 years old) patients infected with the HIV (AIDS) who are diagnosed with DH, by the means of either (i) positive *Histoplasma* antigen in the urine (IMMY monoclonal antibody test); (ii)

confirmation by classical methods (microscopy, culture, or histopathology); or (iii) positive *Histoplasma* qualitative PCR (performed in accordance to [18]) in BAL samples, as well as bone marrow aspirates and tissue samples. Patients who are both antiretroviral treatment (ART) naïve and ART exposed will be recruited.

Exclusion criteria

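### The only named renal and hepatic safety endpoint is a day-14 median percentage change, which does not register how severe toxicity is in a minority, and the DAIDS grades already collected feed no listed endpoint

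*Combined protocol and SAP*

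**What the plan says.** Safety is part of the stated aim in Objectives: "To determine and compare the activity and safety of three regimens of L-AmB". Two toxicity measures appear under Secondary endpoints. One is "Median percentage of change in renal and hepatic function at 14 days will be compared with baseline values". The other is "Frequency of infusion-related toxicity with L-AmB will be recorded".

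Study activities adds that "Clinical and laboratory adverse events will be graded using the NIH DAIDS Toxicity Table [23]". Table 1 schedules chemistry (with magnesium) and blood counts at baseline, day 7 and day 14, and adverse events at days 3, 7 and 14. No listed endpoint uses the grades, the day-7 chemistry, the blood counts or a patient's worst value.

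Statistical analyses gives general rules: "Mean, standard deviation, median, interquartile range and minimum and maximum will be described for continuous variables", and "Categorical variables will be summarized by absolute and relative frequencies". It also lists tests for both kinds of variable. It does not name the renal, hepatic or graded adverse-event data as variables to which these rules apply.

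**The concern.** Renal and hepatic drug toxicity may fall heavily on some patients and spare the rest. The organ-safety question for three dosing schedules is then how many patients in each arm have a serious abnormality. A median change answers a different question, about the typical patient. If a quarter of an arm has large rises, the median is the same whether those rises are 150% or 250%.

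The timing adds to this. An abnormality that peaks around day 7 and recovers by day 14 does not enter the endpoint. A patient who dies before day 14 has no day-14 value, and the protocol gives no rule for that case.

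Research Justification presents the trial as a possible basis for a phase III study. Planning that study would call for a rate of serious toxicity per arm with its uncertainty, and the named endpoint does not supply one.

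**Working it through.** **The plan's own figure.** The only sample-size calculation concerns response. With an expected response of 88% and a 90% interval of ±10 points, n = 1.645² × 0.88 × 0.12 / 0.10² = 28.6, so 29 per arm. Then 29 / 0.90 = 32.2, so 33 per arm and 99 in total. This reproduces. No figure is stated for safety.

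**Assumptions.** The documents give no SD for percentage change and no toxicity rate. I take an SD of 15 to 40 points among unaffected patients, centred on 0, and 25% of an arm severely affected. Who is affected is taken to be independent of where those patients would otherwise have lain.

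**Shift of the median.** If a fraction f has values above all the others, the arm's median becomes the 0.5/(1 − f) quantile of the unaffected patients. The shift is z(0.5/(1 − f)) × SD.

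- f = 0.25: z(0.667) = 0.431.
- f = 8/33: z(0.660) = 0.412.

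| SD (points) | Shift at f = 0.25 (points) |
|---|---|
| 15 | 6.5 |
| 20 | 8.6 |
| 25 | 10.8 |
| 30 | 12.9 |
| 40 | 17.2 |

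The size of the rises does not enter the formula. In simulation (20,000 arms, 8 of 33 affected, SD 20) the median shift was 8.2 points with rises of either 150% or 250%, while the mean shifted by about 36 and 61 points.

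**Sampling noise.** In a toxicity-free arm of 33, the median's 95% sampling range is about ±1.96 × 1.253 × SD/√33 = ±0.43 SD. Simulation gives ±0.42 SD. With 8 of 33 affected, the expected shift of 0.41 SD lies just inside that range. At SD 20 this is 8.2 points against a limit of about 8.5.

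**What the general summaries would show.** I compared two arms of 33 with 25% and 5% affected, SD 20, and affected patients rising by 100% (SD 30). Average results were:

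| Summary | 25% affected | 5% affected |
|---|---|---|
| Upper quartile | about +48% | about +16% |
| Mean | +25% | +5% |
| Maximum | about +142% | about +100% |

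The difference in medians averaged 7.8 points, with a sampling SD of about 8 points. At a two-sided 10% level (my choice, since the plan states no test level), power was about 40% for Mann-Whitney, 64% for the t-test (Welch form) and 63% for Fisher's test on the proportion affected. At 5%, Fisher's power is about 51%.

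**What an incidence endpoint would give.** Exact (Clopper-Pearson) limits:

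- 8/33 = 24%, with a 90% interval of 12.7% to 39.5%.
- 0/33 has a one-sided 95% upper limit of 1 − 0.05^(1/33) = 8.7%.

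**The case against.** The strongest reply is that Statistical analyses already covers this. Creatinine and aminotransferases are continuous, so they would be given a mean, SD, interquartile range, minimum and maximum. DAIDS grades are categorical, so they would be given frequencies, and "Categorical variables will be compared with Fisher exact test or chi-square test, as appropriate". Nothing in that wording excludes the safety data, and the figures above show that those tables would reveal the tail. This stands as far as description goes. It does not supply an endpoint: the general text sets no grade cut-off, no worst-value rule and no denominator, and in an open-label trial these would otherwise be chosen with arm results in view.

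A reader might infer two stronger points, and neither is supported. The first is that the plan cannot tell a toxic arm from a safe one. Mann-Whitney has about 40% power in the scenario above, and the upper quartile, mean and maximum differ plainly. The second is that an incidence has more power than every listed test. The t-test is also listed in the plan and matches Fisher's test there (64% and 63%). In any case Trial design calls the study non-comparative and Statistical analyses calls its comparisons exploratory, so power is a weak yardstick. The case for incidence is that it answers the safety question directly.

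It is also fair to say that Background presents lower haematological and renal toxicity as an advantage of the liposomal form, and that Research Justification regards high single doses as apparently safe. That lowers the expected event rate. It does not remove safety from the objective.

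**Conclusion.** The point holds in a limited form. The named renal and hepatic endpoint does not register the severity of toxicity in a minority. With a quarter of an arm severely affected, it moves by about 0.43 SD, roughly 6 to 17 points for an SD of 15 to 40. At 33 per arm that is about the size of sampling noise. The points figure rests on assumed SDs and an assumed 25% rate. The independence from the size of the rises does not depend on the SD. If the affected patients would have been above the median anyway, the shift is zero.

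The defect is a missing pre-specified incidence endpoint based on grades already collected. It is not an absence of safety data or of other summaries. The sample size is unaffected, because it was set for response.

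**What to change.** Name as the renal, hepatic and laboratory safety endpoint, per arm, the number and proportion of treated patients whose worst post-baseline value through day 14 is a treatment-emergent (worse than baseline) DAIDS grade 3 or higher. Apply it to creatinine, ALT/AST, potassium, magnesium and haemoglobin. Use the day-7 and day-14 chemistry and blood counts plus any unscheduled values. Potassium is assumed to be in the chemistry panel, since Table 1 names only magnesium. Give an exact 90% interval, the confidence level the plan already uses for response, and state that 0/33 would still leave an upper limit of 8.7%.

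Report separately how many patients have no post-baseline laboratory value, including early deaths, and add a sensitivity analysis that counts them as events. Without this, a denominator of all treated patients would silently count early deaths as event-free.

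Keep the median percentage change, with its interquartile range and maximum, as description.

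The cost is analysis wording and a little extra tabulation, because the laboratory tests and grading are already planned. The intervals will be wide at 33 per arm and should be reported as such.

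### The only named renal and hepatic function endpoint is a before-after change, with no baseline-adjusted contrast between the randomised arms to answer the comparative safety objective

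*Combined protocol and SAP*

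**What the plan says.** Secondary endpoints defines the function endpoint in one sentence, as a median percentage change "in renal and hepatic function at 14 days will be compared with baseline values". It names no comparison between arms, effect measure, interval or adjustment.

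The Objectives section is comparative: "To determine and compare the activity and safety of three regimens of L-AmB". Trial design describes a "prospective randomized non-comparative multicenter open label trial".

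Statistical analyses says that "exploratory comparisons will be performed across subgroups" and lists paired tests and between-group tests, ending with "one-way ANOVA or Kruskal-Wallis test, as appropriate and necessary". None of the listed methods takes baseline as a covariate, and none is assigned to the function endpoint.

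Several things besides L-AmB can move these values over the same 14 days. Time for initiating ART says "Physicians will be instructed to initiate ART as soon as possible in AIDS patients with DH". Study activities says "Patients should also be on prophylaxis with daily trimethoprim-sulfamethoxazole" and asks for saline before L-AmB infusion. Under Intervention, itraconazole follows induction in every arm. Exclusion criteria set upper limits on creatinine and urea (1.5 times the upper limit of normal) and on aminotransferases (3 times).

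Other safety evidence is planned: clinical and laboratory adverse events graded by the DAIDS table, and the frequency of infusion-related toxicity.

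**The concern.** A change from baseline within one arm measures everything that happened to those patients over two weeks. The infection is being treated, ART and prophylaxis may be starting, and patients with high entry values have been screened out, so repeat values tend to drift upward. A rise could appear without L-AmB toxicity, and recovery could hide real toxicity.

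The trial has what it needs to deal with the shared part of this. Patients are randomised, arm (iii) receives 3 mg/kg for two weeks, and Table 1 schedules chemistry at baseline, day 7 and day 14. The plan does not say that the arms will be set against each other on this endpoint. At stake is whether the trial can say anything comparative about kidney and liver function under the high-dose regimens, when its results may serve as a basis for a phase III trial.

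**Working it through.** **Plan figures.** The plan gives no figure for this endpoint, so I take n per arm from the primary endpoint. That figure reproduces: 1.645² × 0.88 × 0.12 / 0.10² = 28.57, rounded up to 29; 29/0.9 = 32.2, rounded up to 33; 3 × 33 = 99. I use n = 29.

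**Assumed inputs, not in the documents.** The correlation rho between baseline and day 14, the log-scale SD, the share of candidates cut off by the entry limits, and any common drift.

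**1. Validity.** Simulation with 29 per arm, log SD 0.35, entry cut at +1 SD (15.9% cut off), 3,000 runs per setting and two arms that share any drift:

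| rho | Common drift (log) | Within-arm median change, no effect | Same, true +20% effect | ANCOVA contrast, no effect | ANCOVA contrast, true 0.182 |
|---|---|---|---|---|---|
| 0.5 | -0.10 | -4.7% | +14.2% | -0.001 | 0.182 |
| 0.5 | 0 | +5.3% | +26.7% | 0.000 | 0.183 |
| 0.5 | +0.10 | +16.2% | +39.5% | -0.001 | 0.184 |
| 0.7 | -0.10 | -6.6% | +11.9% | 0.001 | 0.182 |
| 0.7 | 0 | +3.2% | +23.8% | 0.000 | 0.182 |
| 0.7 | +0.10 | +13.9% | +36.7% | 0.000 | 0.184 |

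The true effect is log 1.2 = 0.182. The unadjusted between-arm difference in change also recovered it (0.181 to 0.184; -0.001 to 0.001 under no effect). Randomisation removes the shared bias; adjustment does not.

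**2. Size of the truncation drift alone.** Drift = exp[(1-rho) × SD × φ(z)/(1-c)] - 1, with c the share cut off and z the cut point.
- c = 0.05, φ(z)/(1-c) = 0.1086: 0.9% (rho 0.8, SD 0.4) to 3.3% (rho 0.5, SD 0.6).
- c = 0.10, φ(z)/(1-c) = 0.195: 1.6% (rho 0.8, SD 0.4).
- c = 0.30, φ(z)/(1-c) = 0.497: 16.1% (rho 0.5, SD 0.6), with every input at its extreme.

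The formula is for a log-scale mean, whereas the endpoint is a median.

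**3. Precision.** Standard errors in SD units, equal variances, n = 29. Within-arm mean change: sqrt(2(1-rho)/n). Between-arm change: sqrt(4(1-rho)/n). Between-arm day-14 value: sqrt(2/n). ANCOVA: sqrt(2(1-rho²)/n).

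| rho | Within-arm change | Between-arm change | Between-arm day 14 | ANCOVA | ANCOVA / within-arm |
|---|---|---|---|---|---|
| 0.3 | 0.220 | 0.311 | 0.263 | 0.251 | 1.14 |
| 0.5 | 0.186 | 0.263 | 0.263 | 0.227 | 1.22 |
| 0.7 | 0.144 | 0.203 | 0.263 | 0.188 | 1.30 |
| 0.9 | 0.083 | 0.117 | 0.263 | 0.114 | 1.38 |

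The last column is sqrt(1+rho). Against the within-arm median the gap was narrower in the simulation, but the contrast was still the wider: log-scale SD 0.078 to 0.082 against 0.075 to 0.077 at rho 0.5.

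Against an unadjusted change contrast the variance ratio is (1-rho²)/[2(1-rho)] = (1+rho)/2, a saving of 35%, 25% and 15% at rho 0.3, 0.5 and 0.7. If baseline is truncated to variance v, the ratio is (1-rho²)/[(1-rho)²v + 1-rho²], with rho the correlation before truncation. At 10% cut off, v = 0.712, and rho 0.5 gives 0.75/(0.25 × 0.712 + 0.75) = 0.808. The savings at the same three values of rho become 28%, 19% and 11%; at 30% cut off they are 21%, 14% and 8%.

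**4. What the contrast would deliver.** At rho 0.5 and log SD 0.35, the 90% half-width is 1.645 × 0.227 × 0.35 = 0.131, so an arm ratio is known to within a factor exp(0.131) = 1.14.

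**The case against.** The strongest reply is that the sentence is descriptive. A percentage change is relative to baseline by definition, no test or significance level is named, and nothing says that all change will be put down to the regimen. The trial is labelled non-comparative, the listed tests would allow a Kruskal-Wallis test of change across arms, and graded laboratory events give further safety evidence. Much of this stands. A reader might infer that toxicity as a whole is judged by this endpoint, and the documents do not support that. But the exploratory comparisons are said to be across subgroups, the arms are not named, and no test is tied to this endpoint. Event grades do not supply the missing contrast, and the non-comparative label conflicts with the stated objective.

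A reader might also infer that the randomised contrast isolates L-AmB toxicity without bias. It does not. Itraconazole starts earlier in arms (i) and (ii), saline volume follows the number of infusions, and Rescue therapy provides further L-AmB only in those two arms (8 courses among 66 patients in the plan's pessimistic scenario). Day 14 falls 13 and 11 days after the last planned dose in arms (i) and (ii) (14 - 1 and 14 - 3), but at the end of the course in arm (iii). Deaths or missing values before day 14 could bias the contrast too.

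Finally, the truncation effect is speculative. The renal criterion joins creatinine and urea with an and, which cuts less than either alone. The aminotransferase wording is unclear, and no document gives the share cut off.

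**Conclusion.** The point holds as a gap in the analysis of a secondary safety endpoint. The planned before-after change cannot answer the comparative safety question that the protocol sets, and a randomised contrast is available from data already scheduled. Under the assumed inputs the within-arm figure ran from -6.6% to +16.2% with no effect, and from +11.9% to +39.5% for a true 20% rise. The between-arm contrast was right in each case.

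Three stronger claims are not supported. The contrast is not more precise than the planned quantity: its standard error is 14% to 38% larger than that of the within-arm mean change for rho 0.3 to 0.9, and the gain from adjustment is only over unadjusted between-arm comparisons. Truncation cannot be called a large bias: 16% needs every input at its extreme, and 5% cut off gives 0.9% to 3.3%. The contrast is valid for the assigned strategy when day-14 values are available, and does not measure the effect of L-AmB alone.

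The sample size and the primary analysis are unaffected. The correlation, SD, drift and truncation are my assumptions.

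**What to change.** In Statistical analyses, pre-specify the following and label it exploratory:

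- An ANCOVA of log creatinine and log ALT at day 14 on arm and log baseline, in all randomised patients with day-14 values. Report the ratios (i)/(iii) and (ii)/(iii) with 90% intervals, the level already used for the primary endpoint.
- The within-arm median percentage change as description only, without a test against baseline.
- A statement that the contrast estimates the effect of the assigned strategy: values after rescue L-AmB are included, and itraconazole timing and saline volume differ by arm.
- Deaths and missing day-14 values reported by arm.

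The cost is analysis wording. Baseline and day-14 chemistry are already in Table 1, so no visit, sample or patient is added. An estimate with an interval, marked exploratory, also fits the non-comparative label.
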